## 6 Surveillance procedures

### 6.1 Surveillance method

Subjects in this Surveillance will be enrolled with a central registration system.

### 6.2 Data collection method

Registration and surveillance data for this Surveillance will be collected and recorded in the registration form and survey forms to be supplied by Sponsor.

### 6.3 Contract and logistics

A contract for this Surveillance must be concluded in writing with the head of each site. Contract templates of surveillance site shall be used if available.

[1] The Medical Representative (hereinafter referred to as "MR") shall provide Xeljanz Proper-use Information to doctors, pharmacists, and other relevant site staff who will handle/use Xeljanz.

[Safety information kit]

Product Summary, Proper Use Guide, explanation of "Precautions" for new pharmaceuticals, literature for use by patients, package inserts, etc.

[2] Sponsor will explain the proper use of Xeljanz to each investigator taking part in this Surveillance; after which, the investigator will sign or name/seal the "Confirmation of Cooperation to Surveillance", and submit it to the MR (this document is also required when the investigator is relocated to another site).

[Confirmation of Cooperation to Surveillance]

- Cooperation to diagnosis and treatment of serious infection, tuberculosis and malignant tumor
- Requirements for sites and doctors
- Other relevant items requiring confirmation
- Signature or name/seal of the investigator taking part in this Surveillance

[3] Upon receiving "Confirmation of Cooperation to Surveillance," a contract for this Surveillance will be concluded between the site and Sponsor.

[4] The sample size ratio between the Xeljanz group and the control group to be specified in the contract will be in principle 2 to 1. However, depending on the conditions at the medical facility, the case ratio may be adjusted between 2:1 and 1:1.

[5] Sponsor, upon confirming the conclusion of contract for this Surveillance, shall set up logistics necessary to deliver Xeljanz to the site.

### 6.4 Patient registration

[1] After the date on which the contract for this Surveillance is concluded, the investigator conducting surveillance will complete the registration form provided by Sponsor, and submit the form to Patient Registration Center via FAX.

[Patient Registration Center]

[contact]

Business hours: 9:00 to 17:15 (except for Saturdays, Sundays, National Holidays, and New Year Holidays)

\*FAX transmission after 16:00 will be responded during the following business day.

[2] Definition of start date

(1) Xeljanz group

The date on which administration of Xeljanz begins will be considered the “start date of treatment.” However, for patients participating in the clinical trial, the start date will be considered the date on which administration of the commercially available Xeljanz product begins, and in the case of subjects administered Xeljanz at other medical facilities, it will be the date on which treatment at the physician’s own hospital begins.

(2) Control group

For rheumatoid arthritis patients with poorly controlled disease in spite of continuous use of a methotrexate preparation (MTX) in a dosage exceeding 8 mg/week for 3 months or more, the date on which the change in pharmacotherapy began is regarded as the “start date of surveillance.”

[3] Enrollment method

(1) Xeljanz group

The registration form should be submitted to the Patient Registration Center via FAX in principle no later than 1 week prior to the start of Xeljanz therapy.

If the sponsor has made the judgment that there has been a deviation from the scope of proper use of Xeljanz on the basis of the registration information, this will be checked with the physician in charge of surveillance, and the proper use information will be explained. If any of the patients registered in the control group has been administered Xeljanz during the registration period, the patient will also need to be registered in the Xeljanz group.

(2) Control group

The registration form should be faxed to the Case Registration Center within 2 weeks after surveillance start in the control group.

In principle, case selection in the control group should be performed according to the prescribing conditions for routine medical care under actual use conditions.

Patients to whom any of the following apply will be excluded from candidates for registration in the control group.

- Patients with past experience of treatment with Xeljanz (Patients participating in clinical trial cannot be registered in the control group)
- Patients already registered as part of the control group (Patients switching to another type of pharmacotherapy, excluding Xeljanz will be handled as continued surveillance cases in this survey)

(3) Completion of subject registration

The Case Registration Center will fax the results of registration (eligible/ineligible) to the physician in charge of surveillance.

In the Xeljanz group, the physician in charge of surveillance will begin prescribing after accepting the results on registration eligibility.

(4) Confirmation of cases registered in Xeljanz group

The sponsor will periodically confirm with the physician in charge of surveillance that all Xeljanz cases are

registered. If there are unregistered cases, the physician in charge of surveillance will immediately register the said cases.

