## 7 Survey items and schedule

This Surveillance should be conducted in accordance with the following observation schedule.

Survey item	Observation period	Subject	Registration form	Survey form								
				Booklet 1 *6				Booklet 2	Booklet 3	Booklet 4		
				Pre-dose*1 During treatment*2	Start of surveillance	Month 1	Month 3	Month 6	Month 12	Month 24	Month 36	
Registration form	Confirmation of target patients, prior treatment of MTX, drugs to be investigated, ID number, patient's initials, gender, date of birth or age at the start of treatment, and start date of treatment (or surveillance)	Xeljanz group Control group	Xeljanz group	●	-	-	-	-	-	-	-	
	Contraindication, tuberculosis check, hepatitis B virus test, and clinical laboratory	Xeljanz group		●	-	-	-	-	-	-	-	
Survey Form	Patient characteristics	Both groups	Xeljanz group	-	●	-	-	-	-	-	-	
	Dose record	Both groups		-	↔							
	Concomitant therapy (Pharmacotherapy)	Xeljanz group		-	↔							
	Pneumococcus vaccination*3	Both groups		-	↔							
	Prophylactic administration*4	Both groups		-	↔							
	Chest X-rays or CT	Xeljanz group		-	●	↔		●	●	●	●	
	Tuberculosis check	Xeljanz group		-	●	-	-	-	-	-	-	
	Hepatitis B/C virus test	Xeljanz group		-	●							
	Blood pressures (systolic/diastolic)	Xeljanz group		-	●	-	-	●	●	●	●	
	Clinical laboratory	Xeljanz group		-	●	●	●	●	●	●	●	
	Tender/swollen joint count, patient/doctor-reported outcome, CRP, and ESR	Xeljanz group		-	●	-	-	●	●	●	●	
	Adverse events*5	Xeljanz group		-	↔							
		Control group		-	Serious infection			↔				
	Tests/examinations related to adverse events	Xeljanz group		-	↔							
Follow	Follow-u*6	Both groups		-	Periodically performed for 3 years from the start of treatment for subjects who prematurely discontinue treatment*6							

●: Essential data

\*1: Patients in the Xeljanz group should be registered in principle no later than 1 week prior to the start of treatment.

\*2: Patients in the control group should be registered in principle no later than 2 weeks after the start of surveillance.

\*3: Information on patients in the control group should be collected until 12 months after the start of surveillance.

\*4: Prophylactic administration to prevent tuberculosis, pneumocystis jiroveci pneumonia, and hepatitis B (nucleic acid analogs)

Information on patients in the control group should be collected until 12 months after the start of surveillance.

- Treatment start to Month 6: Malignant tumor and serious infection

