**Table 6. Definitions in the Comparison of Serious Infections**

Term	Definition
Patients without serious infections	Patients who do not correspond to the each definition of patients with serious infections
Time to serious infections during the treatment period (+28 days)	Date of the development of serious infections- date of the initiation of treatment + 1 Both treatment groups will be analyzed for the duration of treatment + 28 days (up to not longer than 1 years).
Censoring period for patients without serious infections during the treatment period (+28 days)	Date of the completion of treatment + 28- date of the initiation of treatment + 1 Both treatment groups will be analyzed for the duration of treatment + 28 days (up to not longer than 1 years).
Time to serious infection during treatment period	Date of the development of serious infection - date of the initiation of treatment + 1 The upper limit is 1 year (366)
Censoring period for patients without serious infections during treatment period	Date of the completion of treatment - date of the initiation of treatment + 1 The upper limit is 1 year (366)
Time to serious infection during overall observation period	Date of the development of serious infection - date of the initiation of treatment + 1 The upper limit is 1 year (366)
Censoring period for patients without serious infections during overall observation period	Date of completion or discontinuation of follow-up - date of the initiation of treatment + 1 The upper limit is 1 year (366)

- **Development of serious infections**

The number of serious infections in each group and the proportion of occurrence are calculated for each SOC and PT. Furthermore, it is calculated for each infection type.

- **Incidence rate of serious infections**

The number of patients with serious infections in each group, incidence rate, and the 95% confidence interval will be calculated in accordance with [Section 8.1.5](#).

In addition, the incidence ratio between treatment groups and the 95% confidence interval and the difference in incidence rate between treatment groups and the 95% confidence interval will be calculated.

The above analyses will be also conducted for serious infections excluding serious herpes zoster and for serious herpes zoster, respectively.

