## 11. APPENDICES

### 11.1. Appendix 1: Details of Data Extraction

#### 11.1.1. Definition of Visit Timing

Day 1: In the Xeljanz group, the oldest initiation date in the status of administration of Xeljanz.

In the control group, the oldest initiation date in the status of drug administration.

Visit timing	Evaluation item	Definition [acceptance range]
Before the initiation of administration	Laboratory test Blood pressure Efficacy observation items	= 'Date of assessment' - 'Date Day 1' + 1 = [-30 - 1] Target date = 1
1 month after the initiation of administration	Laboratory test Blood pressure Efficacy observation items	= 'Date of assessment' - 'Date Day 1' + 1 = [2 - 62] Target date = 31
3 month after the initiation of administration	Laboratory test Blood pressure Efficacy observation items	= 'Date of assessment' – 'Date Day 1' + 1 = [63- 138] Target date=92
6 month after the initiation of administration	Laboratory test Blood pressure Efficacy observation items	= 'Date of assessment' – 'Date Day 1' + 1 = [139- 230] Target date=184
9 month after the initiation of administration	Laboratory test Blood pressure Efficacy observation items	= 'Date of assessment' – 'Date Day 1' + 1 = [231- 321] Target date=275
12 month after the initiation of administration	Laboratory test Blood pressure Efficacy observation items	= 'Date of assessment' – 'Date Day 1' + 1 = [322- 412] Target date=366
15 month after the initiation of administration	Laboratory test Blood pressure Efficacy observation items	= 'Date of assessment' – 'Date Day 1' + 1 = [413- 503] Target date=457
18 month after the initiation of administration	Laboratory test Blood pressure Efficacy observation items	= 'Date of assessment' – 'Date Day 1' + 1 = [504-595] Target date=549

Visit timing	Evaluation item	Definition [acceptance range]
21 month after the initiation of administration	Laboratory test Blood pressure Efficacy observation items	= 'Date of assessment' – 'Date Day 1' + 1 = [596- 686] Target date=640
24 month after the initiation of administration	Laboratory test Blood pressure Efficacy observation items	= 'Date of assessment' – 'Date Day 1' + 1 = [687- 777] Target date=731
27 month after the initiation of administration	Laboratory test Blood pressure Efficacy observation items	= 'Date of assessment' – 'Date Day 1' + 1 = [778- 868] Target date=822

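### Controls may be registered up to 2 weeks after their risk time starts, which can deter registration after an early event and slightly lower the control rate; add a delayed-entry or Day-15 landmark analysis

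*Protocol*

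**What the plan says.** **Xeljanz group.** Under Protocol 6.4 the registration form is due "in principle no later than 1 week prior to the start of Xeljanz therapy", and "the physician in charge of surveillance will begin prescribing after accepting the results on registration eligibility". The sponsor periodically confirms that all Xeljanz cases are registered: "If there are unregistered cases, the physician in charge of surveillance will immediately register the said cases". The main comparison uses the MTX adherent comparative set (SAP 5.1.2 and 8.2.3.1), which takes only new patients. SAP 5.1.1 defines these as patients whose first Xeljanz dose came after registration.

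**Control group.** Protocol 6.4 states: "The registration form should be faxed to the Case Registration Center within 2 weeks after surveillance start in the control group". The footnote to the schedule in Protocol 7 is softer: "Patients in the control group should be registered in principle no later than 2 weeks after the start of surveillance". Protocol 6.4 asks that controls be selected in line with routine prescribing. It gives no consecutive-enrolment rule and no completeness check for them.

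**The clock.** For controls, Protocol 6.4 says that "the date on which the change in pharmacotherapy began is regarded as the" start date of surveillance. SAP 11.1.1 sets Day 1 in the same way: "In the control group, the oldest initiation date in the status of drug administration". In SAP Table 6 the time to serious infection is "Date of the development of serious infections- date of the initiation of treatment + 1". Tables 5 and 7 treat malignancy and death alike. The registration date enters none of these definitions.

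**The concern.** Whether a control joins the survey can be settled after that patient's risk time has begun. Suppose a patient starts a new drug, is admitted with pneumonia on Day 8, and has not yet been faxed in. The physician may then never register that patient, and nobody checks. Controls who are registered on, say, Day 12 bring 12 days of follow-up that tend to be event-free because of how they came to be registered. In the main comparative set, Xeljanz patients bring no such time.

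If this happens, the control rate is too low and the Xeljanz-to-control ratio too high. The effect is largest for serious infection, because that comparison runs for only 1 year and the first 2 weeks weigh more. The covariates in SAP 6.3 describe patients at baseline, so weighting on them cannot remove selection that depends on what happens after the start. Comparing malignant tumors and serious infections with control is a stated objective (Protocol 1, SAP 2.2).

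**Working it through.** **The plan's own figure.** The documents give no number on this point. Their expected 104 malignancies does fix the dropout pattern to use: with linear loss to 50% at 3 years, 4000 × 3 × 0.75 × 0.0116 = 104.4.

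**Inputs from the documents.** Control registration up to 14 days after start (Protocol 6.4 and 7); infection window 366 days (SAP Table 6); 3-year window 1096 days (SAP 11.1.1); 4000 Xeljanz and 2000 control patients; malignancy rate 1.16 per 100 person-years and 50% dropout at 3 years (Protocol 3).

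**Assumptions.** The documents do not give the shape of the early hazard, the spread of registration delays, the fraction of early events lost, or a serious-infection rate. Each is varied below.

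**Formulas.** With Weibull shape k and rare events, the share of 1-year control events in the first 14 days is (14/366)^k. If the delay is uniform over 0 to 14 days, the share falling before registration is (14/366)^k / (k + 1). If a fraction f of those events is lost, a true ratio of 1.00 reads 1 / (1 − f × share).

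**Serious infection, 1 year.**

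| Shape k | Share, all registered on Day 14 | Ratio, f = 1 | Ratio, f = 0.5 | Share, uniform delay | Ratio, f = 1 | Ratio, f = 0.5 |
|---|---|---|---|---|---|---|
| 1.0 (constant) | 3.8% | 1.04 | 1.02 | 1.9% | 1.02 | 1.01 |
| 0.8 | 7.3% | 1.08 | 1.04 | 4.1% | 1.04 | 1.02 |
| 0.7 | 10.2% | 1.11 | 1.05 | 6.0% | 1.06 | 1.03 |

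As a cross-check, take a hazard that is m times higher in the first 14 days, all controls registered on Day 14 and f = 1. The share is 14m / (14m + 352). For m = 2 it is 7.4% (ratio 1.08), and for m = 3 it is 10.7% (ratio 1.12). With the protocol's dropout spread linearly, the ratios for m = 1, 2 and 3 are 1.04, 1.09 and 1.13.

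**Malignancy and death, 3 years.** 14/1096 = 1.3%, so the ratio is at most 1.01 at constant hazard. With m = 3 the share is 42 / (42 + 1082) = 3.7% and the ratio 1.04.

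**In events.** 2000 controls contribute 2000 × 14 / 365.25 = 76.7 person-years in the first 14 days. At 1.16 per 100 person-years that is 0.9 of the 2000 × 2.25 × 0.0116 = 52 expected control malignancies. At assumed infection rates of 1 to 8 per 100 person-years it is 0.8 to 6.1 infections. Losing all of them at constant hazard moves the log ratio by 0.15 to 0.42 of its standard error.

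**Cost of a Day-15 start.** First-year control time is 2000 × (1 + 5/6) / 2 = 1833 person-years, and 76.7 / 1833 = 4.2%. Dropping the same time in both groups raises the standard error of the log rate ratio by 1 / √(1 − 0.042) = 1.022, about 2.2%.

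**The case against.** The strongest reply is that the plan does not exclude these patients. The only control exclusions are past Xeljanz use or trial participation and earlier control registration. The control form records a start date already past (Protocol 7.1), so a control with a Day 8 event can still be registered. Loss of such patients is a conjecture about behaviour. A physician filling a contracted control number might even register a patient because the event made the case memorable. This stands: a reader might infer that an early event bars registration, but the text supports only that it can deter it, and the direction is likely rather than proven.

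Xeljanz registration before dosing is also only in principle, and missed cases are registered late, so some Xeljanz patients in the wider comparative set have pre-registration time too. This stands for that set. It does not rescue the main set, which takes only patients first dosed after registration. Late registration of missed Xeljanz cases is also required whether or not an event occurred.

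A reader might further infer that registration beyond 2 weeks makes matters worse. The enrollment-violation exclusion in SAP 5.1.1, carried into 5.1.2, may remove such patients, so that cannot be claimed. It does not touch the permitted 14 days.

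The SAP's version 8.0 change entry places sensitivity analyses of the group comparison in section 8.2.3.1.4, and the text after 8.2.3.1.3 is redacted. They may already deal with early follow-up. Finally, SAP 4 calls all tests exploratory, which lowers the stakes but does not correct an estimate.

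**Conclusion.** The asymmetry is in the text, and it reaches the main comparison. Its likely effect is small. For 1-year serious infection, a true ratio of 1.00 would read about 1.02 to 1.06 if delays are uniform and all pre-registration events are lost, and less if only some are. The figures of 1.04 at constant hazard and 1.08 to 1.11 under assumed Weibull shapes 0.8 and 0.7 are ceilings. They need every control registered on Day 14 and every early event lost. For 3-year malignancy and death the effect is about 1.01 at constant hazard.

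A reader might infer that the hazard ratio is inflated by about 10%, or that the comparison is invalid. The documents support neither: they give no hazard shape, delay distribution or count of lost events. Nor is death part of the stated comparative objective; it is a comparison that the SAP adds.

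The point still deserves a cheap answer. SAP 6.1.1 already leaves out post-survey deaths so that the groups are compared fairly, because such deaths tend to be collected in the Xeljanz group only. One-sided timing of registration is a problem of the same kind.

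**What to change.** If the redacted section already handles early follow-up, confirming that is enough. Otherwise add to SAP 8.2.3.1, for serious infection and also for malignancy and death, one of the following:

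- a Cox and IPTW analysis in which each control enters the risk set on the registration date, with time since treatment start kept as the time scale; or
- a Day-15 landmark in both groups, limited to patients who are registered, event-free and under observation on that day.

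Give matching crude rates and Kaplan-Meier curves. Report the result beside the existing main analysis, not in its place: SAP version 10.0 was written after the database release, so a change to the main models now would be post hoc. List control events dated before registration instead of dropping them from the safety reporting.

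The landmark gives up about 4% of 1-year control person-time and makes the standard error about 2% larger. Sites, sample size and data collection do not change. The registration date is not among the items listed in Protocol 7.1, so it must be obtainable from the registration center. Neither version recovers the events of patients who were never registered. Each only stops the time before registration, or before Day 15, from counting in favour of the control group.

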## 6.5 Observation period

### [1] Xeljanz group:

- (1) Registered subjects up to a certain sample size exceeding 3000 subjects from the start of registration: 3 years (36 months) from the date of treatment start
- (2) Registered subjects after the above (1): Only 6 months from the date of treatment start

### [2] Control group: 3 years (36 months) from the date of treatment start

### [3] Type of survey form

Booklet-type survey form will be used for this Surveillance.

Safety and effectiveness will be evaluated on the day of the initial office visit after the end of the observation period for each booklet (including the day on which the observation period ends). However, the safety and effectiveness will be evaluated based on the information from the last known visit if the subject is lost to follow up during the treatment period.

The effectiveness evaluation will be performed on Xeljanz group only.

### [4] Follow-up surveillance

For a period of 3 years from the date of treatment start, follow-up surveillance for subjects in the Xeljanz group (1) and the control group will be conducted on the information related to the drug administration conditions and adverse events after discontinuation (serious infections [12 months], malignant tumors, adverse events leading to death).

Booklet No.	Observation period	Safety		Effectiveness		
		Xeljanz group	Control group	Xeljanz group	Control group	
Booklet 1 d)	Treatment start to Month 6 d)	All adverse events	Serious infection, Malignant tumor, Death	Before treatment start, At Month 6	-	
Booklet 2	Months 7 to 12			At Month 12		
Booklet 3	Months 13 to 24		Malignant tumor, Death	At Month 24		
Booklet 4	Months 25 to 36			At Month 36		
Follow-up survey form d)	Performed for 3 years from the start of treatment for subjects who prematurely discontinue treatment d)					

d) For subjects who correspond to “[1] Xeljanz group (2)”; the observation period will be only the duration of 6 months from the date of treatment start (Booklet 1) and no follow-up surveillance will be conducted.

